# 2.2.2 Modified intention-to-treat population (mITT)

The mITT population is all subjects who were injected at least once with the study treatment, who received at least one day of GSC therapy during the study, for whom a primary Target Treatment limb has been defined and who have the primary efficacy outcome assessed at Week 6 after the second injection (i.e. Visit 6).

# 2.2.3 Per Protocol population (PP)

The PP population is all subjects included in the mITT population for whom no major protocol violations/deviations occurred.

# 2.3 Safety

The safety population is all subjects who were injected at least once with the study treatment.

## 2.4 Pharmacokinetics

Not applicable for the study.

# 2.5 **Primary population**

The primary analysis of the final analysis based on the primary efficacy endpoint will be performed on the mITT population. In addition, ITT and PP analyses will be performed as secondary analyses.

# **3 STATISTICAL METHODS**

# 3.1 Statistical analysis strategy

The statistical analyses will be performed in accordance with international conference on harmonisation (ICH) E9 guideline and will be based on the pooled data from the individual study sites, unless otherwise stated.

All statistical analyses described in this statistical analysis plan (SAP) will be performed by the Clinical Research Organisation (CRO) Biotrial managed by the sponsor's Biometry Department.

# 3.1.1 Primary efficacy endpoint

The primary efficacy endpoint is the percentage of responder subjects at Week 6 after the second injection, according to composite AROM in the primary TT limb.

The composite AROM  $(X_A)$ , regardless of whether the muscle groups were injected or not, as measured by goniometer in the primary TT limb (either UL or LL, depending on which one has been selected as the primary TT limb), will be calculated as follows:

- composite  $X_A$  UL:  $X_A$  UL =  $X_{AEF} + X_{AWF} + X_{AFF}$
- composite  $X_A LL$ :  $X_A LL = X_{ASol} + X_{AGN}$

where for UL: EF=elbow flexors, WF=wrist flexors and FF=extrinsic finger flexors,

# and for LL: Sol=soleus and GN=gastrocnemius muscles.

The definition of a responder is the following: a subject will be considered a responder if he/she achieves at least the predefined improvement threshold - larger or equal to  $35^{\circ}$  in UL or  $5^{\circ}$  in LL - in the primary TT limb (based on the composite AROM individual change from baseline to Week 6 after the second injection).

# 3.1.2 Secondary efficacy endpoints and exploratory endpoint

The secondary efficacy endpoints are as follows:

- the percentage of responder subjects at Week 6 after the first injection, according to composite AROM in the primary TT limb (based on the composite AROM individual change from baseline to Week 6 after the first injection)
- AROM against 10 prespecified muscle groups, 5 in upper and 5 in lower limbs: mean change from baseline at Week 6, Week 12, re-injection visit and last study visit only
- composite AROM against injected muscle groups (any of the 10 prespecified), in upper and lower limbs: mean change from baseline at Week 6, Week 12, re-injection visit and last study visit only
- full composite AROM against five UL muscle groups or full composite AROM against five LL muscle groups or overall full composite AROM against ten prespecified muscle groups, regardless of whether the muscle groups were injected or not:
  - mean change from baseline at Week 6, Week 12, re-injection visit and last study visit only
  - the full composite AROM will be calculated as follows:
    - (1) full composite  $X_A$  UL:  $X_A$  full UL =  $X_{ASE} + X_{AEF} + X_{AWF} + X_{AFF} + X_{APT}$
    - (2) full composite  $X_A$  LL:  $X_A$  full  $LL = X_{ASol} + X_{AGN} + X_{AGM} + X_{AHS} + X_{ARF}$
    - (3) overall full composite  $X_A$ :  $X_A$  full =  $X_{ASE} + X_{AEF} + X_{AWF} + X_{AFF}$ +  $X_{APT} + X_{ASol} + X_{AGN} + X_{AGM} + X_{AHS} + X_{ARF}$

where for UL: SE=shoulder extensors, EF=elbow flexors, WF=wrist flexors, FF=extrinsic finger flexors and PT=pronator teres, and for LL: Sol=soleus, GN=gastrocnemius muscles, GM=gluteus

maximus, HS=hamstrings and RF=rectus femoris.

- active UL function measured using MFS: mean change from baseline in MFS overall score (i.e. mean score over the 10 tasks assessed locally and centrally by a reviewer blinded regarding the order of the video recording/visit number for a given subject) at Week 12 after each injection cycle and last study visit.
- active LL function measured using maximal WS barefoot without walking aids or, if absolutely necessary, with a cane, measured using a 10-metre WST: mean change from baseline at Week 12 after each injection cycle and last study visit.
- subject satisfaction with the GSC: at baseline (only for patients who had GSC performed previously), Week 6, Week 12, re-injection visit and last study visit only
- changes in subject's beliefs that the GSC will help to improve functional capacity: change from baseline to Week 6, Week 12, re-injection visit and last study visit only

- changes in physiotherapist's belief that the GSC will help to improve functional capacity: change from baseline to Week 6, Week 12, re-injection visit and last study visit only
- subject compliance with the GSC: the percentage of days over study period when GSC therapy was performed (as determined from the subject diary) will be summarized in percentage and in classes (<80% and 80-100%).
- global assessment of benefits, evaluated by both the investigator and the subject (or caregiver): at the end of each cycle
- in subjects with an injection planned at Week 16 or 20 of each cycle: satisfaction with longer interval between 2 injections collected at the corresponding re-injection visit or the last cycle visit
- quality of life changes, measured using the EQ-5D-5L and SF-12 scales:
  - change from baseline to last study visit.
  - the analysed scores for the EQ-5D-5L questionnaire will be:
    - (1) the score answered at each question of the questionnaire: Mobility score, Self-care score, Usual activities score, Pain/discomfort score and Anxiety/depression score,
    - (2) Index score (for the French centers and the US centers only),
    - (3) EQ-5D-5L VAS score.
  - the analysed scores for the SF-12 questionnaire will be the SF-12 physical score and SF-12 mental score.

The exploratory efficacy endpoint is the correlation between full composite AROM and active function (MFS (Local and central review) in UL and WS in LL): Week 12 after each injection cycle and last study visit.

# 3.1.3 Safety endpoints

The safety endpoints are:

- Treatment Emergent Adverse Events (TEAEs), including information on seriousness, intensity, drug relationship and TEAE associated with premature withdrawal of study medication; Serious Adverse Events (SAEs);
- Clinical safety endpoints: physical examination and vital signs.

# 3.1.4 Multiplicity

No multiple testing will be performed in this study.

# 3.1.5 Significance testing and estimation

The statistical analysis of efficacy is only descriptive therefore no formal statistical significance testing will be performed and all the analyses will be primarily descriptive in nature. When appropriate and unless otherwise specified, two-sided 95% CIs will be displayed and if p-values are presented, they will be for exploratory purposes only. For the 95%CIs of proportions, the Agresti-Coull interval will be used.

#### 3.2 Analysis methods

# 3.2.1 Efficacy

All efficacy data will be included in the subject data listings for the Enrolled population.

## 3.2.1.1 Primary efficacy analyses

The analyses of the primary efficacy endpoint will be performed on the mITT population for the primary efficacy analysis, and on the ITT and PP populations for the secondary efficacy analyses in support of the primary efficacy analysis.

# 3.2.1.1.1 Primary efficacy analysis of the primary efficacy endpoint

A frequency table of the percentage of responder subjects at Week 6 after the second injection will be provided on the mITT population with the two-sided 95% CI.

# 3.2.1.1.2 Secondary efficacy analyses of the primary efficacy endpoint

A frequency table of the percentage of responder subjects at Week 6 after the second injection will be provided on the ITT population (including the two-sided 95% CI) where subjects with missing responder status at Week 6 after the second injection will have their last postbaseline responder status used instead. Subjects with no postbaseline responder status will be considered nonresponders. The number of imputed data and the number of missing data will be provided.

The time to first response will be defined as the time elapsed from the date of first injection in the study to the date of first response (response as defined in section 3.2.14). For subjects who have a nonresponder status until the last study visit or for dropouts and lost to follow-up subjects, their data will be censored at the time of their last study visit.

The time to first response will be analysed using the Kaplan-Meier (KM) survival analysis method on the ITT population. The median survival time and the 95% CI of the median will be estimated using KM product-limit estimation. The time to first response will also be illustrated graphically using KM's estimates to display the cumulative rate of first response with the number of subjects at risk.

The following SAS® code will be used:

PROC LIFETEST data = ADTTE(where = (ittfl="Y")) METHOD=km;

TIME aval\*cnsr(1);

RUN;

Additionally, a frequency table of the percentage of responder subjects at Week 6 after the second injection will be provided on the PP population with the two-sided 95% CI.

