- at Week 12: the investigator will decide if the subject is still responding to treatment or if a further injection is needed, based on his/her clinical judgement. If a further injection is needed, the subject completes the study after study assessments have been performed (before the injection outside the study is given) (i.e. Final Visit). If a further injection is not needed, the subject will return at Week 16;
- at Week 16: the investigator will again decide if the subject is still responding to treatment or if a further injection is needed, based on his/her clinical judgement. If a further injection is needed, the subject completes the study after study assessments have been performed (before the injection outside the study is given) (i.e. Final Visit). If a further injection is not needed, the subject will return at Week 20;
- at Week 20: the subject completes the study after study assessments have been performed, regardless of whether a further injection is needed (i.e. Final Visit).

[figure not shown]
The overall duration of the study for each subject will be between 24 and 40 weeks (from Baseline Visit to Final Visit).

Subjects who receive two AbobotulinumtoxinA administrations and complete the required postinjection FU visits will be considered to have completed the study.

Subjects who withdraw from the study before completion of scheduled visits will have Early Withdrawal Visit assessments performed at their last visit.

PROTOCOL FINAL (INCLUDING AMENDMENT #2): 24 JANUARY 2018

PAGE 29/105

PROTOCOL FINAL (INCLUDING AMENDMENT #2): 24 JANUARY 2018

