3.5 Study Duration

This study will consist of two open-label injection (treatment) cycles. Each cycle will include postinjection FU visits of up to 20 weeks (see Section 3.1). Subjects are expected to participate in this study for a minimum of 24 weeks (if they have postinjection FU visits up to Week 12 only, following both injections) and a maximum of 40 weeks (if they have postinjection FU visits up to Week 20, following both injections).

The subject's participation in the study will be considered to have ended at the time of the Final Visit. This will be no later than 20 weeks after the second AbobotulinumtoxinA injection.

The overall duration of the study will be between approximately 15 and 18 months. The study will be considered to have started when the first subject provides signed informed consent.

The study will be considered to have ended after the last subject has completed his/her Final Visit.

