Each subject will also receive a personalised GSC and will be asked to perform daily GSC therapy throughout the study, including the recording in a diary of the performed exercises of the prescribed GSC therapy. Telephone calls will be made to the subject every 2 weeks to check how the GSC therapy is being performed and that the diary is being filled out every day.

In Cycle 1, postinjection follow-up (FU) visits will be held after the first AbobotulinumtoxinA administration, as follows:

• at Week 6;

[figure not shown]
- at Week 12: the investigator will decide if the subject is still responding to treatment or if a second injection is needed, based on his/her clinical judgement. If a second injection is given, this marks the start of Cycle 2 (see below). If a second injection is not given, the subject will return at Week 16;
- at Week 16: the investigator will again decide if the subject is still responding to treatment or if a second injection is needed, based on his/her clinical judgement. If a second injection is given, this marks the start of Cycle 2 (see below). If a second injection is not given, the subject will return at Week 20;
- at Week 20: the investigator will again decide if the subject is still responding to treatment or if a second injection is needed, based on his/her clinical judgement. If a second injection is given, this marks the start of Cycle 2 (see below). If the investigator decides that a second injection should not be given, based on his/her clinical judgement, the subject will be withdrawn from the study.

[figure not shown]
In Cycle 2, postinjection FU visits will be held after the second AbobotulinumtoxinA administration, as follows:

- at Week 6;
- at Week 12: the investigator will decide if the subject is still responding to treatment or if a further injection is needed, based on his/her clinical judgement. If a further injection is needed, the subject completes the study after study assessments have been performed (before the injection outside the study is given) (i.e. Final Visit). If a further injection is not needed, the subject will return at Week 16;

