#### (12) **Time to first response**

The time to first response will be calculated as (date of first response or date of last study visit - date of first injection) + 1. For subjects who have a responder status, the date of first response will be used. For subjects who have a nonresponder status until the last study visit or for dropouts and lost to follow-up subjects, the date of last study visit will be used.

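### The Kaplan-Meier curve for time to first response censors nonresponders at a design-dependent study completion, so after about Week 24 it probably overstates response to two injections

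*SAP*

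**What the plan says.** SAP 3.2.1.1.2 adds a time-to-first-response analysis on the ITT population. Time runs from the first injection to the first visit at which the composite AROM threshold is met (35° in UL, 5° in LL). One rule covers completers and dropouts alike: "For subjects who have a nonresponder status until the last study visit or for dropouts and lost to follow-up subjects". For every one of these groups the SAP states that "their data will be censored at the time of their last study visit". Appendix 1 (12) repeats the rule. The numerical output is the median with its CI, and the figure is to "display the cumulative rate of first response with the number of subjects at risk". No end point for the curve is set, and no sensitivity analysis for the censoring is planned.

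Follow-up length varies by design. Protocol 3.1: "The overall duration of the study for each subject will be between 24 and 40 weeks". Protocol 3.5 explains the lower limit: "a minimum of 24 weeks (if they have postinjection FU visits up to Week 12 only, following both injections". Injection 2 is given at Week 12, 16 or 20. At Week 12 or 16 of Cycle 2 the investigator's judgement decides who leaves: "If a further injection is needed, the subject completes the study after study assessments have been performed" (SAP 1.2). The others stay to the next visit, and Cycle 2 Week 20 is final for all. Separately, a subject judged at Cycle 1 Week 20 not to need injection 2 is withdrawn (Protocol 3.1 and 3.6).

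**The concern.** Kaplan-Meier assumes that a subject censored at a given week has the same later chance of a first response as those still at risk. Two features of the design work against this after Week 24.

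- **Re-injection timing.** A subject re-injected at Week 12 can complete at Week 24, having already failed the Cycle 2 Week 6 visit (Week 18) and the Cycle 2 Week 12 visit. A subject re-injected at Week 20 reaches Cycle 2 Week 6 only at Week 26. The product-limit step at Week 26 comes from the second kind of subject and is credited to the first.
- **Clinical judgement.** Those who leave at Cycle 2 Week 12 or 16 are judged to need another injection. Those who remain are judged still to be responding.

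At stake is the right-hand part of Figure 14.2.1.2.2.2 and any cumulative rate read from it. Elsewhere the SAP keeps subjects without a responder status in the denominator as nonresponders: in the ITT responder analysis those with no post-baseline status, and after injection 1 those with a missing Week 6 status. The curve could therefore show a visibly higher rate than a simple count of responders.

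**Working it through.** **The plan's own figure.** The documents give no number for this analysis. The sample size reproduces: 1.96² × 0.60 × 0.40 / 0.08² = 144.05, rounded up to 145; 145 / 0.95 = 152.6, rounded up to 153.

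**Inputs.** Visit paths are those of Protocol Table 3, with N = 153. All of the following are assumptions, because the documents have no such data.

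- Chance of first response among those not yet responding: Cycle 1 Week 6, 0.40; Cycle 1 Week 12, 0.15; Cycle 1 Week 16 or 20, 0.08; Cycle 2 Week 6, 0.25; Cycle 2 Week 12, 0.10; Cycle 2 Week 16 or 20, 0.05.
- Base case: 60/25/15% for re-injection at Week 12/16/20, and the same split for the final visit at Cycle 2 Week 12/16/20.
- No dropout and no Week 20 withdrawal.

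**The mechanism at Week 26, base case.**

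- Re-injected at Week 12, never responding, completing at Week 24: 153 × 0.60 × 0.60 × 0.85 × 0.75 × 0.90 × 0.60 = 19.0 censored.
- At risk just after Week 24: 58.5 − 3.5 events − 19.0 = 36.0.
- Re-injected at Week 20 and not yet responding: 153 × 0.15 × 0.60 × 0.85 × 0.92 × 0.92 = 9.9. Only these have a visit at Week 26, and 25% respond, giving 2.48 events.
- Kaplan-Meier applies 2.48 / 36.0 = 6.9% to everyone not yet responding, including the 19.0 who have left. That credits 19.0 × 0.069 = 1.3 subjects, or 1.3 / 153 = 0.9 points, to subjects who had no visit due.

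**The curve over time, base case.** Full follow-up means everyone is observed to Cycle 2 Week 20, with the same late chance of response for those who left as for those who stayed.

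| Week | At risk | 1−KM % | In-study share % | Full follow-up % |
|---|---|---|---|---|
| 16 | 78.0 | 50.6 | 50.6 | 50.6 |
| 24 | 58.5 | 64.1 | 64.1 | 64.1 |
| 26 | 36.0 | 66.5 | 65.7 | 65.7 |
| 32 | 16.8 | 70.8 | 67.8 | 69.5 |
| 40 | 1.0 | 73.6 | 68.0 | 70.3 |

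**Week 40, 1−KM minus full follow-up (points)**, by the late chance of response in early completers relative to those who stay:

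| Re-injection split | Final-visit split | Equal | Double | Fourfold |
|---|---|---|---|---|
| 60/25/15 | 60/25/15 | +3.3 | +1.1 | −3.0 |
| 60/25/15 | 33/34/33 | +2.7 | +1.2 | −1.7 |
| 33/34/33 | 60/25/15 | +2.5 | +0.4 | −3.6 |
| 33/34/33 | 33/34/33 | +2.0 | +0.6 | −2.2 |
| 90/7/3 | 60/25/15 | +3.4 | +1.1 | −3.2 |
| 90/7/3 | 33/34/33 | +3.1 | +1.5 | −1.6 |

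With equal late response the excess is 2.0 to 3.4 points here, and other assumed visit-level rates take the upper end to 4.9. If Cycle 2 response is lower in late re-injected subjects (halved after Week 16 re-injection, quartered after Week 20), the base-case excess falls to 66.7 − 66.3 = 0.4 points. If early completers would never respond later, it is 73.6 − 68.0 = 5.6 points in the base case.

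**Week 20 withdrawal.** If 20% or 50% of nonresponders reaching Cycle 1 Week 20 without re-injection are withdrawn, 1−KM exceeds the in-study share at Week 24 by 0.1 to 0.4 points in the base case, and by up to 1.1 with a 33/34/33 re-injection split.

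**The case against.** **The gap to the in-study share is not bias.** A reader might take the difference between 1−KM and the proportion who ever responded in the study (73.6% against 68.0% above) as the error. It is not. Whenever events follow censoring, 1−KM exceeds that proportion, even when censoring is independent and Kaplan-Meier is correct. With first-response chances set by calendar week alone and exit at random, Kaplan-Meier is unbiased and the gap still runs from 2.9 to 10.6 points. Only the comparison with full follow-up measures bias.

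**The direction is not certain.** A reader might also infer that the curve is always too high and always favours treatment. The documents do not support that. They hold no late-response data. The event is an AROM threshold, while exit follows clinical judgement, so their link among never-responders is assumed. The sign reverses at a fourfold late chance in early completers. Week 20 withdrawal is a further response-related exit and may act in the opposite direction.

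**Completion is not clearly a competing event.** It ends observation and does not prevent a response. Coding every exit without response as a competing event would simply return the in-study proportion, which answers a different question.

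**The stakes are limited.** This is a supportive, descriptive analysis added in the SAP. Numbers at risk will be displayed, and no Week 40 rate is announced.

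All of this stands, and it limits the claim. It does not restore independent censoring: the Week 26 step arises from the visit schedule whatever clinical judgement adds. A reversal would require subjects just judged to need another injection to respond much more often, without it, than those kept on. Numbers at risk show that the tail is thin but do not correct it.

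**Conclusion.** The point holds as a limited one. Censoring at completion is dependent by design, and after about Week 24 the curve probably overstates response to two injections. The size is roughly 2 to 5 points at Week 40. That rests on assumed visit-level rates and re-injection splits, equal late response in early completers and no dropout; it illustrates the effect and does not bound it. The excess is close to nil if late re-injected subjects respond poorly in Cycle 2, and negative if early completers would have responded much more often later. Up to Week 24 the curve is sound apart from ordinary dropout and the small Week 20 withdrawal effect. The primary endpoint and both Week 6 responder tables are untouched. The median is untouched if half the subjects respond before Week 24; in the base case it falls at Week 16.

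**What to change.** In SAP 3.2.1.1.2, and for Figure 14.2.1.2.2.2 and Table 14.2.1.2.2.1:

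- Limit the displayed Kaplan-Meier curve, and any rate read from it, to about Week 24, the minimum planned follow-up. State the exact day. The Week 12 visits allow +7 days in each cycle, so the earliest completions spread from Week 24 to Week 26.
- Add a table of the cumulative ever-responder proportion by protocol visit (Cycle 1 Week 6, Week 12, re-injection; Cycle 2 Week 6, Week 12, last visit), with the ITT denominator and labelled as the in-study proportion.
- Note that the curve treats Week 20 withdrawals without re-injection as censored, and report their number.

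The censoring rule in Appendix 1 (12) can stay, with a cross-reference to the cut-off. The cost is SAP wording, a shorter curve and one extra table. No new data are needed.
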